### 10.1.2. PHARMACOKINETIC PARAMETERS

Subjects with partial data will be evaluated on a case-by-case basis to determine if sufficient data are available for reliable estimation of PK parameters. Pharmacokinetic parameters following database lock will be calculated for HMPL-523 (and its metabolites, including but not limited to M1 and M44) by noncompartmental methods, using actual elapsed time from dosing.

For PK parameter calculations following single dose (Day 1 of Cycle 1), predose samples that are BLQ or missing will be assigned a numerical value of zero. Any anomalous concentration values observed at predose on Day 1 of Cycle 1 will be identified in the study report and used for the computation of PK parameters. If the anomalous concentration is greater than 5% of  $C_{max}$ , the PK parameters for the given subject will be calculated and reported in the listing and considered on a case-by-case basis for exclusion from statistical summaries and analyses. Any other BLQ concentrations will be assigned a value of zero if they precede quantifiable samples in the initial

---

Document: 2018-523-00US1 PK SAP Final V1.0\_22Jun2023.docx

PPD

Version Number: Final 1.0

Version Date: 22Jun2023

CCI

### Statistical Analysis Plan for Pharmacokinetics

portion of the profile. A BLQ value that occurs between quantifiable data points, especially prior to  $C_{max}$ , will be evaluated to determine if an assigned concentration of zero makes sense, or if exclusion of the data is warranted. Following  $C_{max}$ , BLQ values embedded between two quantifiable data points will be treated as missing when calculating PK parameters. If a BLQ value occurs at the end of the collection interval (after the last quantifiable concentration), it will be set to zero. If consecutive BLQ concentrations are followed by quantifiable concentrations in the terminal portion of the concentration curve, these quantified values will be excluded from the PK analysis by setting them to missing, unless otherwise warranted by the concentration-time profile, and the consecutive BLQ concentrations will also be set to missing.

The following single dose plasma PK parameters will be calculated (if estimable) on Day 1 of Cycle 1 (C1D1) for HMPL-523 (and metabolites if applicable) following QD dosing for Stage 1 and Stage 2:

$C_{max}$	Maximum concentration, obtained directly from the observed concentration versus time data.
$t_{max}$	Time to maximum concentration, obtained directly from the observed concentration versus time data.
$AUC_{0-t}$	Area under the concentration-time curve from time zero (predose) to time of last quantifiable concentration, calculated by linear up/log down trapezoidal summation.
$AUC_{tau}$	Area under the concentration-time curve during a dosing interval, tau (tau = 24 h), calculated by linear up/log down trapezoidal summation. Note: The following conventions will be followed for the calculation of the parameter: 
 
• <math>AUC_{all}</math> will be used as an estimate of <math>AUC_{tau}</math> if concentrations fall to BLQ at or before reaching tau unless otherwise warranted by the data. For this, the BLQ will be set to zero.
 
• This parameter will not be calculated if the data is missing at tau.
 
• If the time deviation at time tau is significant, the analyst may consider listing the <math>AUC_{tau}</math> estimate but excluding the estimate (and related parameters) from summaries and analyses.
 

$C_{max}/D$	Dose-Normalized $C_{max}$ , calculated as $C_{max}$ divided by dose.

Document: 2018-523-00US1 PK SAP Final V1.0\_22Jun2023.docx

PPD

Version Number: Final 1.0

Version Date: 22Jun2023

CCI

 Statistical Analysis Plan for Pharmacokinetics
 

---

$AUC_{\tau}/D$	Dose-Normalized $AUC_{\tau}$ , calculated as $AUC_{\tau}$ divided by dose.
----------------	--

The following plasma PK parameters will be estimated for HMPL-523 (and metabolites if applicable) following multiple dosing on Days 15 and 28 of Cycle 1 for Stage 1 and Day 28 of Cycle 1 (and 14-28 days after a dose change in subsequent cycles) for Stage 2 where data is collected and available:

$C_{\max}$	Maximum concentration after multiple dosing, obtained directly from the observed concentration versus time data.
$t_{\max}$	Time of maximum concentration, obtained directly from the observed concentration versus time data.
$C_{\min}$	Minimum observed concentration after multiple dosing, obtained directly from the observed concentration versus time data.
$t_{\min}$	Time of minimum concentration, obtained directly from the observed concentration versus time data.
$AUC_{\tau}$	
Area under the plasma concentration-time curve during a dosing interval (<math>\tau = 24</math> h), calculated by linear up/log down trapezoidal summation. Actual elapsed time will be used for the calculation, unless otherwise specified below.
 
The following conventions will be followed for missing or BLQ data at <math>\tau</math> on study Days 15 and 28 (Cycle 1):
 
 
• If the concentration at predose is missing, then the concentration will be set to equal the concentration measured at <math>\tau</math> [assuming linear PK and steady-state conditions, and that the <math>\tau</math> sample was collected within a window of <math>\pm 1</math> hour of the scheduled time postdose for the calculation of <math>AUC_{\tau}</math> but prior to the next dose].
 
• If no sample is collected at the end of the dosing interval or data are missing at the end of the dosing interval, the concentration will be set equal to the predose value (assuming linear PK and steady-state conditions, and that the predose collection was valid) and <math>\tau</math> will be set to the nominal time for the calculation of <math>AUC_{\tau}</math>, if appropriate.
 
• <math>AUC_{\text{all}}</math> (if appropriate) shall be used as an estimate of <math>AUC_{\tau}</math> if
 

Document: 2018-523-00US1 PK SAP Final V1.0\_22Jun2023.docx

 PPD
 [REDACTED]

Version Number: Final 1.0

Version Date: 22Jun2023

 CCI
 [REDACTED]
[REDACTED]
[REDACTED]

 Statistical Analysis Plan for Pharmacokinetics
 

---

	
concentrations fall to BLQ at or before reaching tau unless otherwise warranted by the data. For this the BLQ will be set to zero.
 
 
If the time deviation at time tau is significant (outside of the window of <math>\pm 1</math> hour of the scheduled time postdose), the parameter will not be calculated.
 

$C_{avg}$	Average concentration over the dosing interval tau, calculated as $AUC_{tau}$ divided by the dosing interval, tau [tau: 24, actual time will be used. See above for window for 'tau'].
PTR	Peak to trough ratio, calculated as $C_{max}/C_{min}$
$R_{A(AUC)}$	Accumulation ratio, calculated for $AUC_{tau}$ on Days 15 and 28 as $[AUC_{tau}$ on C1Dx / $AUC_{tau}$ on C1D1], where x is Day 15 or Day 28.
$R_{A(C_{max})}$	Accumulation ratio, calculated for $C_{max}$ on Days 15 and 28, as $[C_{max}$ on C1Dx / $C_{max}$ on C1D1], where x is Day 15 or Day 28.
$t_{1/2,eff}$	Effective half-life, calculated as $-0.693 * tau / \ln(1 - 1/R_{A(AUC)})$
TimeHigh	Time above the $IC_{90}$ level of 123 ng/mL
CL/F	Apparent systemic clearance, calculated as dose divided by $AUC_{tau}$ . (Only for HMPL-523).
$C_{max}/D$	Dose-Normalized $C_{max}$ .
$AUC_{tau}/D$	Dose-Normalized $AUC_{tau}$ .
$MRC_{max}$	Ratio of metabolite $C_{max}$ to parent HMPL-523 $C_{max}$ , calculated for each metabolite as (metabolite $C_{max}$ /metabolite MW) / (parent $C_{max}$ /parent MW).
$MRAUC_{tau}$	Ratio of metabolite $AUC_{tau}$ to parent HMPL-523 $AUC_{tau}$ , calculated for each metabolite as (metabolite $AUC_{tau}$ /metabolite MW) / (parent $AUC_{tau}$ /parent MW).
$M/T RAUC_{tau}$	Ratio of metabolite $AUC_{tau}$ to total drug $AUC_{tau}$ , calculated for each metabolite as (metabolite $AUC_{tau}$ /metabolite MW) / (parent $AUC_{tau}$ /parent MW + metabolite M1 $AUC_{tau}$ /metabolite M1 MW + metabolite M44 $AUC_{tau}$ /metabolite M44 MW).

C=cycle; D=Day; MW=molecular weight

Concentrations as supplied by the bioanalytical laboratory will be used in the PK analysis. The units of concentration and resulting PK parameters, with amount or concentration in the unit, will

Document: 2018-523-00US1 PK SAP Final V1.0\_22Jun2023.docx

PPD

Version Number: Final 1.0

Version Date: 22Jun2023

CCI

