5.3.4 Dosage, Administration, and Compliance

Dose levels to be potentially tested in this study include 100, 200, 400, 600, and 800 mg/day orally.

The proposed dose of HMPL-523 is as specified in HMPL-523 should be taken with approximately 8 ounces (240 mL) of water under fed conditions, ideally within 30 minutes after meal but not later than 90 minutes after a meal (Table 1). Patients are advised to take QD dosage as required in cohorts/groups. All efforts should be made to ensure that the patient takes HMPL-523 at approximately the same time every day during their participation in the study and ideally within a ± 4 -hour window.

HMPL-523 should be taken with approximately 8 ounces (240 mL) of water under fed conditions, ideally within 30 minutes after meal but not later than 90 minutes after a meal (Table 1). The administration time should be accurately recorded in the patient diary.

In the study, patients will not be allowed to make up missed doses during any calendar day; patients will resume dosing at their next scheduled dose.

Guidelines for dosage modification and treatment interruption or discontinuation are provided in Sections 5.4 and 5.7.

Any overdose or incorrect administration of the study drug should be noted on the patient's source documentations and case report form (CRF). AEs associated with an overdose or incorrect administration of the study drug should be recorded on the patient's source documents and the AE page of the CRF.

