APPENDIX 2 PK SAMPLING TIME POINTS (ONCE DAILY) (DOSE ESCALATION STAGE)^d

Visit Cycle and Day	Time Point
Cycle 1 Day 1	Pre-dose ^a
	30 minutes (± 5 minutes) post-dose
	1 hour (± 5 minutes) post-dose
	2 hours (± 10 minutes) post-dose
	4 hours (± 15 minutes) post-dose
	6 hours (± 15 minutes) post-dose
	8 hours (± 15 minutes) post-dose
Cycle 1 Day 2	Pre-dose ^a
Cycle 1 Day 15	Pre-dose ^a
	30 minutes (± 5 minutes) post-dose
	1 hour (± 5 minutes) post-dose
	2 hours (± 10 minutes) post-dose
	4 hours (± 15 minutes) post-dose
	6 hours (± 15 minutes) post-dose
	8 hours (± 15 minutes) post-dose
Cycle 1 Day 16	Pre-dose ^a
Cycle 1 Day 28 ^b	Pre-dose ^a
	30 minutes (± 5 minutes) post-dose
	1 hour (± 5 minutes) post-dose
	2 hours (± 10 minutes) post-dose
	4 hours (± 15 minutes) post-dose
	6 hours (± 15 minutes) post-dose
	8 hours (± 15 minutes) post-dose
Cycle 2 Day 1 ^c	Pre-dose ^a

PK = pharmacokinetic.

^a The blood samples will optimally be obtained within 5 minutes prior to dosing but may be obtained up to 30 minutes prior to dosing.

^b Cycle 1 Day 28 shares the window with Cycle 2 Day 1, which is ± 3 days and should be immediately followed by Cycle 2 Day 1.

^c Cycle 2 Day 1 pre-dose is the 24-hour (± 15 minutes) PK sample of Cycle 1 Day 28.

^d Blood samples that remain after PK analysis of HMPL-523 may be used exclusively for exploratory biomarker purposes.

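### On Days 15 and 28 the PK SAP may calculate AUCtau when the 24-h sample is missing but never when it is more than 1 h off time, which on Stage 1 Day 15 can discard protocol-compliant data

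*SAP*

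**What the plan says.** PK SAP section 10.1.2 treats the end-of-interval (tau, 24 h) sample differently by day and by what went wrong.

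- **Days 15 and 28, sample missing.** If no sample was collected "or data are missing at the end of the dosing interval, the concentration will be set equal to the predose value", tau is set to nominal and AUCtau is calculated. This holds only where appropriate, "assuming linear PK and steady-state conditions, and that the predose collection was valid".
- **Days 15 and 28, sample off time.** Outside a window of ±1 "hour of the scheduled time postdose), the parameter will not be calculated". No fallback is given.
- **Day 1, sample missing.** AUCtau is not calculated.
- **Day 1, sample off time.** "If the time deviation at time tau is significant, the analyst may consider listing the" AUCtau estimate and leaving it out of summaries. Here 'significant' is not defined.

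For Days 15 and 28 the general time basis is: "Actual elapsed time will be used for the calculation, unless otherwise specified below".

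The protocol sets the sampling times. In Appendix 2 the Day 15 tau sample is the Cycle 1 Day 16 predose draw, timed only against the next dose: "The blood samples will optimally be obtained within 5 minutes prior to dosing but may be obtained up to 30 minutes prior to dosing". Section 5.3.4 asks that the patient "takes HMPL-523 at approximately the same time every day during their participation in the study and ideally within a" ±4-hour window. By contrast, the Day 28 tau sample (Cycle 2 Day 1 predose) is tied to 24 h, with ±15 min in Appendix 2 and +15 min in Appendix 3.

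**The concern.** A patient with no 24-h sample may keep a steady-state AUCtau. A patient with a valid predose sample at, say, 22.5 h may not, although the second profile carries more information.

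Losing AUCtau also loses Cavg, CL/F, AUCtau/D, RA(AUC), t1/2,eff, MRAUCtau and M/T RAUCtau for that profile. AUCtau, CL/F and the accumulation ratio are named PK outcome measures in protocol section 4.8.3. Stage 1 cohorts after the first start at 3 patients, and the PK SAP shows only n, minimum and maximum when n is below 3. One discard in such a cohort therefore removes its mean and geometric mean. The individual value is also lost to the dose-proportionality model in section 10.1.3.

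The off-time rules differ between Day 1 and Days 15/28 as well, so the two parts of RA(AUC) are handled differently.

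**Working it through.** The documents give no figure for the number or effect of off-time samples, so there is nothing to reproduce. The check has two parts.

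**1. Can compliant conduct trigger the discard?**

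- *Stage 1 Day 15:* yes. If the Day 15 dose is at the usual time and the next dose is up to 4 h either side, the Day 16 predose draw falls at about 20 to 28 h, or up to 30 min earlier. No 24-h tolerance is stated for it.
- *Day 28, both stages:* no. A sample more than 1 h from 24 h already breaches the 15-min window, so the SAP's ±1 h is the more lenient rule.
- *Day 1:* the mandatory discard does not apply.

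**2. Are the discarded data usable?** This part is an illustration.

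*Inputs*
- Half-lives of 9.8 and 13.5 h: the range in protocol section 2.2.4.1 (healthy volunteers).
- Half-life of 17.0 h: the SAP's effective half-life formula at the mean accumulation ratio of 1.60 in protocol section 2.2.4.5, that is -0.693 × 24 / ln(1 - 1/1.60) = 17.0 h.
- Sampling at 0, 0.5, 1, 2, 4, 6 and 8 h plus the tau sample (Appendix 2), with linear up/log down AUC (PK SAP).
- Assumed: one-compartment oral model without noise, once-daily steady state, and ka set so that single-dose Tmax is 4 h.

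*Formula.* For a tau sample at time ts, λ = ln(C8/Cts)/(ts - 8) and C24 = C8 × exp(-16λ). AUC0-24 is then calculated with C24.

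*Results at Tmax 4 h, error against the true AUC0-24:*

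| Tau sample | Error |
|---|---|
| On time at 24 h | -0.3% to -0.8% |
| At 20 to 28 h, brought to 24 h | -0.3% to -0.9% |
| Missing, predose substituted, previous dosing gap 24 h | -0.4% to -0.8% |
| Missing, predose substituted, previous gap 28 or 20 h | -5.6% to +4.4% |
| At 20 or 28 h, AUC left at actual time | -11.7% to +9.2% |

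Against the AUC from an on-time sample, the corrected value differs by -0.05% to +0.08% at steady state (previous gap 24 h) and by -0.06% to +0.10% after a first dose.

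*Slower analyte.* Protocol section 2.2.4.5 gives one range of median Tmax, among the analytes whose names are redacted, that reaches 8.0 h. With Tmax 8 h, the corrected value differs from the on-time value by -1.3% to +1.8% at steady state and by -1.8% to +2.6% after a first dose. At steady state the on-time AUC is itself low by 1.8% to 3.8% against the truth, because sampling is sparse after 8 h.

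**The case against.** The best defence is that the rules cover different situations. Predose substitution is conditional, not automatic. The off-time rule also catches samples drawn after the next dose, which cannot be used directly. The last table row shows that an off-time AUC left at actual time can be wrong by about 10%, so some rule is needed. Day 1 must differ on missing samples, because predose substitution cannot work after a first dose. All of this stands. None of it explains why a sample drawn before the next dose should be discarded when no sample at all may still yield a result.

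A reader might infer more than the documents support:

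- *That protocol timing generally permits off-time tau samples.* This holds for the mandatory discard only on Stage 1 Day 15. Day 28 is the only routine steady-state profile in Stage 2, and there an off-time sample is a deviation.
- *That Day 1 profiles are also thrown away.* An off-time Day 1 estimate may still be listed.
- *That a dose level vanishes from the summary.* The n, minimum, maximum, listings and scatter plots remain, as do Cmax, tmax, Cmin and any valid AUCtau from another day.
- *That discards are frequent.* The ±4 h is an upper tolerance worded as an ideal, and no count of off-time samples is given. Protocol section 2.2.4.5 leaves 800 mg out of its steady-state summary because few parameters could be calculated, but gives no reason.

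The simulation also favours log-linear correction by construction. The Tmax 8 h run partly tests this, and the error grows there but stays modest.

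**Conclusion.** The point holds in limited form. For Days 15 and 28 the PK SAP permits a potentially less accurate AUCtau from a missing sample and forbids a usually accurate one from an off-time sample drawn before the next dose. Protocol-compliant data can be lost only for the Stage 1 Day 15 profile. On Day 28 the inconsistency affects samples that are already deviations.

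The cost per discard is AUCtau and seven dependent parameters, plus the mean and geometric mean if the cohort falls below 3. The total cost cannot be determined from the documents. That the data are recoverable rests on a one-compartment, noise-free model with half-lives of 9.8 to 17.0 h. These are secondary and exploratory PK objectives, so this is a worthwhile, inexpensive correction and not a threat to the trial's main conclusions.

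**What to change.** Replace the last AUCtau bullet for Days 15 and 28 with:

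> *If the tau sample was drawn before the next dose but outside 24 h ±1 h, AUC0-24 will be calculated using a 24-h concentration obtained by log-linear interpolation (late sample) or extrapolation (early sample) from the last preceding quantifiable sample at or after Cmax and the actual-time sample. The value will be flagged in listings, and a summary without flagged values will be provided. If the sample was drawn after the next dose, it will be treated as missing, and the missing-sample rule applies only if its stated conditions are met, including a predose sample taken about 24 h after the previous dose.*

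Three related changes:

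- Apply the same interpolation rule to off-time Day 1 samples drawn before the next dose, so that both parts of RA(AUC) cover 0 to 24 h.
- Keep the Day 1 rule of no calculation when the sample is missing.
- Use 24 h as the Cavg divisor only where AUC has been brought to 24 h.

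The cost is PK SAP wording and a partial-area calculation, with no new samples. The downside is that a few AUCtau values rest on an estimated 24-h concentration. The modelled change is about 0.1% at Tmax 4 h. At Tmax 8 h it is up to about 2% at steady state and 2.6% on Day 1.

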2.2.4.4 Study 2015-523-00CH1 Phase I Study in Patients with Relapsed/Refractory Lymphoma

This study was completed on 30 September 2021. Overall, 134 patients were enrolled in the study. Twenty-seven patients were treated in the dose escalation phase, including 7 patients in the 200-mg QD cohort, 3 patients in the 400-mg QD cohort, 6 patients in the 600-mg QD cohort, 3 patients in the 800-mg QD cohort, and 8 patients in the 200-mg BID cohort. One hundred seven patients were treated in the dose expansion phase, including 32 patients in the 400-mg QD cohort and 75 patients in the 600-mg QD cohort. During the dose expansion phase, RP2D was 600 mg QD for patients whose weight was > 65 kg and 400 mg QD for patients whose weight was ≤65 kg.

Safety

CCI

Pharmacokinetics

CCI on Day 1, Day 15, and Day 28 following multiple 200 to 800 mg QD and 200 mg BID HMPL-523 in the dose escalation phase, and 400 mg QD and 600 mg QD doses in the dose expansion phase, in Chinese patients with relapsed or refractory mature B-cell tumor. In this study, all patients were instructed to take HMPL-523 at approximately 30 minutes after a meal.

Median T_{max} values for HMPL-523 ranged from 3.00 to 5.97 hours following 200 to 800 mg QD doses, and from 1.98 to 3.88 hours following multiple 200 mg BID doses. The mean ARs for AUC_{tau} on Days 15 and 28 ranged from 1.27 to 2.65 following multiple 200 to 600 mg QD doses, and from 1.97 to 2.52 following multiple 200 mg BID doses. In general, lower C_{max} , similar C_{min} , and higher AR for AUC_{tau} were observed with 200 mg BID dosing compared to 400 mg QD dosing.

CCI with the increased HMPL-523 doses from 200 to 800 mg QD and 200 mg BID. Median T_{max} values were similar between QD and BID dosing regimen, generally 4.00 hours post-dose CCI and ranging from 1.93 to 4.08 hours post-dose CCI. The mean AR for AUC_{tau} on Days 15 and 28 ranged from 1.22 to

3.25 CCI, and 0.426 to 1.52 CCI, following multiple 200 to 600 mg QD doses, and from 2.40 to 3.34 CCI, and 1.79 to 1.88 CCI following multiple 200 mg BID doses. In general, lower C_{max} , similar C_{min} and higher AR for AUC_{tau} were observed with 200 mg BID dosing compared to 400 mg QD dosing.

following multiple 200 to 600 mg QD or 200 mg BID doses.

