There were limited calculable PK parameters at steady state at 800 mg QD; therefore, the data are excluded from the summary described below. Following multiple oral doses of HMPL-523 from 100 to 700 mg QD, the median T_{max} values for HMPL-523 ranged from 3.0 to 6.0 hours post-dose. The exposure of HMPL-523 (maximum plasma concentration at steady state [$C_{max,ss}$] and area under the drug concentration-time curve over the dose interval at steady state [$AUC_{tau,ss}$]) increased in approximately dose-proportional manner over the dose range of 100 to 700 mg QD. The apparent oral clearance at steady state ranged from 189 to 304 L/h for doses from 100 to 700 mg QD. HMPL-523 reached PK steady state by Day 15. The mean AR was approximately 1.60 (ranging from 1.21 to 2.01) following multiple 100 to 700 mg QD doses.

The exposure of the CCI with increased HMPL-523 doses. Median T_{max} values for CCI ranged from 4.0 to 8.0 hours, and 2.0 to 4.0 hours post-dose, respectively, following multiple doses of 100 to 800 mg QD. The mean ARs of $AUC_{tau,ss}$ CCI were approximately 1.86 and 1.55, respectively. The mean CCI ratios of $AUC_{tau,ss}$ were approximately CCI respectively. The mean CCI ratios of $AUC_{tau,ss}$ were approximately CCI respectively.

Efficacy

As of the data cut-off date (10 May 2022), this study was still ongoing. No efficacy data was available.

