## Statistical Analysis Plan for Pharmacokinetics

---

be presented as they are received from the bioanalytical laboratory.

$C_{max}$ ,  $C_{min}$ ,  $t_{max}$ , and  $t_{min}$  will be obtained directly from the concentration-time profiles. In case of multiple peaks, the highest postdose concentration will be reported as  $C_{max}$ . In case of multiple peaks of equal magnitude, the earliest  $t_{max}$  will be reported.

For calculation of the metabolite ratio,  $C_{max}$  and  $AUC_{tau}$  will be adjusted by molecular weight (MW) of the parent drug and metabolite. The MWs are presented below:

- HMPL-523 [ $C_{24}H_{30}N_6O_3S$ ]: 482.60 g/mol (free base)
- M1 or HM5023222 [ $C_{24}H_{30}N_6O_4S$ ]: 498.60 g/mol
- M44 or HM5025866 [ $C_{31}H_{38}N_6O_{11}S$ ]: 702.73 g/mol

Based on the formulation for HMPL-523, no dose adjustment calculations need to be made for any molecular conversions between administered drug product and analyte measured.

Scatter plots of individual and geometric mean PK parameters [ $C_{max}$ ,  $AUC_{tau}$ ,  $C_{max}/D$ , and  $AUC_{tau}/D$ ] will be presented for Cycle 1 Days 1, 15, and 28 to assess the relationship between dose and PK exposure for HMPL-523 and its metabolites.

Pharmacokinetic parameters for HMPL-523 and its metabolites will be summarized for the PKAS by stage, cohort/dose level, cycle, and day using N, n, arithmetic mean, SD, CV, minimum, median, maximum, geometric mean (GeoMean), and geometric CV (GCV) using the PK analysis set. If  $n < 3$ , then only n, minimum, and maximum will be presented. Arithmetic mean, SD, CV, GeoMean, and GCV will not be calculated for  $t_{max}$  and  $t_{min}$ . A subject listing of individual PK parameters for each treatment will be provided. Stage 2 PK parameters calculated from serial sampling concentration data collected after a dose change will only be included in listings.

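### The PK SAP's effective half-life has no value for a patient whose accumulation ratio is 1 or less, no rule covers that case, and the group summary loses its lowest accumulators

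*SAP*

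**What the plan says.** PK SAP 10.1.2 lists t1/2,eff among the multiple-dose parameters: "Effective half-life, calculated as" -0.693 × tau / ln(1 - 1/RA(AUC)), with tau 24 h. RA(AUC) is the patient's own ratio: "Accumulation ratio, calculated for $AUC_{tau}$ on Days 15 and 28 as" AUCtau on that day over AUCtau on Cycle 1 Day 1. Nothing constrains this ratio to exceed 1.

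The list covers the parent and, conditionally, the metabolites: "The following plasma PK parameters will be estimated for HMPL-523 (and metabolites if applicable) following multiple dosing on Days 15 and 28" of Cycle 1 in Stage 1, and Day 28 in Stage 2. Only CL/F is restricted to the parent.

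The same section then says: "Pharmacokinetic parameters for HMPL-523 and its metabolites will be summarized for the PKAS by stage, cohort/dose level, cycle, and day". The statistics are N, n, mean, SD, CV, minimum, median, maximum, geometric mean and geometric CV. Below three observations, only n, minimum and maximum are shown.

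The section has rules for BLQ values, missing predose or end-of-interval samples, and time deviations. An estimability qualifier is attached to the Day 1 list ("The following single dose plasma PK parameters will be calculated (if estimable) on Day 1 of Cycle 1 (C1D1"), but not to the multiple-dose list. Case-by-case review is for patients with partial data.

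On size, Protocol 2.2.4.5 reports for this study: "The mean AR was approximately 1.60 (ranging from 1.21 to 2.01) following multiple 100 to 700 mg QD doses".

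**The concern.** An observed RA(AUC) is a ratio of two AUCs, each measured with error and each varying from day to day. A patient who accumulates little can show a ratio of 1 or less from two complete, valid profiles. The formula then needs the logarithm of zero or of a negative number, and no t1/2,eff exists.

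Because t1/2,eff rises with RA, the missing values are always those that would rank lowest. Missingness is therefore determined by the quantity being summarised, and each mean, median or geometric mean rests on a subset selected by outcome. The loss is largest where accumulation is smallest, so comparisons between dose levels or disease groups could be distorted.

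This is the only half-life among the PK SAP's parameters. Terminal half-life was removed from the protocol's PK outcome list in Amendment 2 (Protocol Appendix 18).

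**Working it through.** The documents give no t1/2,eff value, so there is no stated figure to reproduce.

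**Inputs.** The formula and tau = 24 h are from PK SAP 10.1.2. Mean accumulation ratios of 1.21, 1.60 and 2.01 are from Protocol 2.2.4.5. The variability of RA is not in the documents. I assume log-normal AUCs with a within-patient CV of 20% to 40%, independent between Day 1 and the later day, a common underlying RA within a group, and the reported mean taken as the median of RA.

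**Step 1: where the formula has a value.** The numerator is 0.693 × 24 = 16.632.
- RA 0.9: 1 - 1/0.9 = -0.111, no logarithm.
- RA 1.0: ln(0), undefined (the limit is 0 h).
- RA 1.01: 3.6 h. RA 1.10: 6.9 h.
- RA 1.21: 1 - 1/1.21 = 0.1736, ln = -1.751, so 16.632/1.751 = 9.5 h.
- RA 1.60: 1 - 1/1.60 = 0.375, ln = -0.981, so 17.0 h.
- RA 2.01: 1 - 1/2.01 = 0.5025, ln = -0.688, so 24.2 h.

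The function increases with RA, so the values lost at RA ≤ 1 are the lowest-ranked.

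**Step 2: share of patients lost.** ln RA has SD s = sqrt(2 × ln(1 + CV²)), which is 0.280, 0.415 and 0.545 at AUC CV 20%, 30% and 40%. This corresponds to a CV of RA of about 29% to 59%. The share lost is Φ(-ln(RA)/s). For example, at RA 1.21 and CV 20%, Φ(-0.191/0.280) = Φ(-0.68) = 25%.

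**Step 3: summary of the patients who remain.** Simulated with 2,000,000 draws of RA, keeping RA > 1.

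| Underlying RA (formula value) | AUC CV | Share lost | Geometric mean of the rest | Arithmetic mean of the rest |
|---|---|---|---|---|
| 1.21 (9.5 h) | 20% | 25% | 11.4 h | – |
| 1.21 | 30% | 32% | 13.7 h | – |
| 1.21 | 40% | 36% | 16.1 h | – |
| 1.60 (17.0 h) | 20% | 5% | 16.7 h | 18.5 h |
| 1.60 | 30% | 13% | 18.2 h | 21.5 h |
| 1.60 | 40% | 19% | 20.5 h | 25.6 h |

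At RA 2.01 with a CV of RA itself of 20% to 30%, at most 0.9% are lost and the geometric mean is 23.4 to 23.7 h against 24.2 h.

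**Step 4: how often a group is touched.** At RA 1.60 and AUC CV 30% (12.9% lost), the chance of losing at least one patient is 1 - 0.871^6 = 56% with 6 patients. With 25, the size of the HL cohort in Protocol Table 2, it is 1 - 0.871^25 = 97%.

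**Step 5: deletion versus skewness.** At RA 1.60 with a CV of RA of 50%, the arithmetic mean of the remaining patients is 23.1 h. Counting the lost patients as 0 h still gives 19.4 h. So of the rise over 17.0 h, 19.4 - 17.0 = 2.4 h is skewness and 23.1 - 19.4 = 3.7 h is deletion.

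**Step 6: alternatives.** Applying the formula once to the group geometric mean RA gives 9.5, 17.0 and 24.2 h with nobody dropped. A median that ranks the lost patients lowest returns 9.5 h at RA 1.21 and 17.0 h at RA 1.60.

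**The case against.** The strongest reply is that the size is assumed and the parameter is minor. The documents give no CV for RA, so how often RA falls to 1 or less is not known. The largest figures apply at RA 1.21, and the protocol does not say which dose level that was. The 100 mg cohort may hold a single patient (Protocol 4.2), in which case nothing would be averaged. N and n are both shown, individual values are listed, and RA(AUC) is summarised with its geometric mean. An attentive reader could see the gap and compute the group value. All of this stands, and it limits the point. However, n below N shows that values are missing, not why, and it does not correct the summary.

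A reader might infer three stronger claims that the documents do not support.

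- *That half-life is always overstated.* At RA 1.60 and AUC CV 20% the geometric mean is 16.7 h, just below 17.0 h, because values just above RA = 1 are very short.
- *That the typical patient has no metabolite value.* Metabolites are included only if applicable, and Protocol 2.2.4.5 gives mean accumulation ratios of about 1.86 and 1.55 for the other analytes in this study. The low group mean ("0.426 to 1.52 CCI, following multiple 200 to 600 mg QD doses") is for a redacted analyte in study 2015-523-00CH1. It shows only that a group mean below 1 can occur with this drug.
- *That dropping patients would explain a value longer than the 9.8 to 13.5 h in Protocol 2.2.4.1.* That is elimination half-life in healthy volunteers, and RA 1.60 already gives 17.0 h with nobody dropped.

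**Conclusion.** The gap is certain: the formula has no value at RA(AUC) of 1 or less, the plan summarises individual values, and no rule covers the case. Followed as written, the plan removes the lowest accumulators from each summary.

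The size is conditional on the assumed AUC CV of 20% to 40%. It is material at RA near 1.2, with a geometric mean 20% to 70% above the formula value (11.4/9.5 = 1.20; 16.1/9.5 = 1.69). At RA 1.60 it runs from nil to about 21% (20.5/17.0). At high RA or low CV it is negligible. Metabolites are affected only if t1/2,eff is derived for them.

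This is a minor, inexpensive improvement. t1/2,eff is not among the PK outcome measures in Protocol 4.8.3, the RP2D is already set, and no dose, safety or efficacy conclusion depends on it.

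**What to change.** Add to PK SAP 10.1.2:

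- For each summary group (dose level in Stage 1; disease group and overall in Stage 2) and day, derive t1/2,eff by applying the formula to the geometric mean RA(AUC). Alternatively, report a median that ranks patients with RA of 1 or less lowest.
- Keep individual values in listings, show RA of 1 or less as 'not estimable', and report the number of such patients beside each group value.
- Report no t1/2,eff for a group or analyte whose geometric mean RA is 1 or less.
- If a confidence interval is given by transforming that of the geometric mean RA, report its lower limit as not estimable when the RA limit is 1 or less. This will happen in small groups: at RA 1.21 with 6 patients, the 95% lower limit, 1.21 × exp(-2.571 × s/√6), is 0.90, 0.78 and 0.68 at AUC CV 20%, 30% and 40%.

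The cost is a few sentences and one table change, with no new data. With the geometric-mean approach, no between-patient CV is shown for t1/2,eff. RA(AUC) and its variability are still summarised, so little is lost.
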